### Sample size and power

This is a pilot RCT, and the primary outcomes of this study are: 1) to test the feasibility and acceptability of the crowdsourced intervention, and 2) to pilot the preliminary impact of crowdsourced PS intervention in promoting HIV testing among partners of the newly identified HIV cases. In addition, this pilot RCT aimed to collect preliminary data for the designing of a full RCT, which aimed to measure the efficacy of the crowdsourced PS intervention in promoting PS. Thus, the sample size of this study is not designed and will be not powered enough to test the difference between the two arms. However, with a sample size of 120 (80 for intervention arm and 40 for the control arm, respectively), this pilot study would collect enough information to measure the feasibility and acceptability of the intervention, and it will be able to observe the differences between the two arms and collect preliminary data for an adequate sample size calculation of a full RCT. With a sample size of 120 (ratio of 2:1), alpha=0.05, power=0.80, and the partner return rate in the conventional PS arm is 30% (around 31% in 2016 in Guangzhou), the minimal detectable effect size would be 26.7% for this pilot study.

### Intervention

Crowdsourced PS procedures: After randomization, the procedures for the crowdsourced intervention arm will be explained to the MSM HIV index cases in this arm. Final procedures will be determined upon completion of crowdsourcing events. The expected procedures are shown below:

1. MSM in the intervention arm will *receive the crowdsourced intervention* at the study site.
2. Index MSM will *choose specific crowdsourced materials* to use for notification of each partner.
3. The index cases will then *choose the procedure* to be used for delivery of the intervention: a) personally send to partner, b) have the study coordinator send, c) have the CBO send, d) send through an anonymous email/phone number system, or e) any combinations of the above-mentioned procedures.  
The crowdsourced intervention package may be delivered by text, WeChat, gay dating apps, and/or email. If the index is not ready to send the message to the partner at the time of the clinic visit, he may contact the research coordinator at any time within 6 weeks to request that the materials be sent.
4. The index patients will *select a message* about the crowdsourced intervention. The texts/emails will include a unique ID, address of the center, and phone number/WeChat ID of the study coordinator at the center. The specific content will be refined in the crowdsourcing events.
5. *The message will be sent to the partners* through a prechosen delivery channel, coupled with prechosen crowdsourced intervention materials.
6. *Partners* who view the intervention materials *will be prompted* to enter a phone number, email address, WeChat ID, and usernames for Blued (A popular gay dating mobile application with 43 million users in China). These data allow us to link partners who view the intervention materials to the index cases.
7. At the conclusion of the intervention materials, *information will be provided* about the MSM community centers where HIV testing is available, research coordinator's contact information, and instructions to retain the email/text to present at the center. If the partner is willing to provide a phone number or email address, *a message will be automatically generated* including the center and coordinator information.
8. *Partners will be encouraged* to present for testing within one week of notification.

9. *Index MSM will also be given PS cards*, comparable to the standard PS arm, in case they choose to inform partners this way

In addition, after introducing the crowdsourced intervention to the participants in this group, a short survey that aims to evaluate the feasibility and acceptability of the crowdsourced intervention will be carried out.

Conventional PS procedures: The index cases in the conventional PS arm will be provided with referral cards that include the unique ID to link index and partners, as well as the address of the study centers where they can present for free HIV testing and the phone number of the study coordinator. The index cases will be encouraged to remind their partners to bring the referral card with them when they present. On the reverse side of the card, we will provide instructions to facilitate forwarding of test results if the partner chooses to attend a different clinic. Guangzhou CDC will also coordinate with other clinics in the city to collect the cards and a brief consent to capture the HIV result.

Partner linkage: Partners will be linked to the indexes through the unique ID on the referral cards. Partners without unique ID information will be matched to the index using a sequential matching algorithm using all index identification information provided. If a partner is unable to produce the card/text/email, we will ask him/her how he/she was originally notified of the need for testing. If the partner indicates he/she was informed by intervention materials, we will ask him/her to identify the phone number, email address, or username to which the message was delivered. We will also ask him/her to provide the date that he reviewed the intervention materials. If a partner was given a referral card but cannot present the card, we will ask him/her to give the name or contact information of the person who gave him/her the card. We will also obtain the date that the card was provided. Partners without card/text/email will be matched to the index using a sequential matching algorithm using all index identification information provided.

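### HIV tests done at other clinics are actively captured for referral cards but not for texts and emails, so partner testing may be under-counted in the intervention arm; size unknown, cheap to fix

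*Combined protocol and SAP*

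**What the plan says.** The Primary outcomes section counts two kinds of tested partner: those who come to the centers, and those confirmed in the CDC's central medical record database. Neither source is limited to one arm.

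In the Intervention section, the paragraph on conventional PS procedures adds an active route for tests at other clinics, and describes it for cards. On the back of the card, "we will provide instructions to facilitate forwarding of test results if the partner chooses to attend a different clinic". In addition, "Guangzhou CDC will also coordinate with other clinics in the city to collect the cards and a brief consent to capture the HIV result".

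For messages, step 4 of the crowdsourced procedures lists the content: "The texts/emails will include a unique ID, address of the center, and phone number/WeChat ID of the study coordinator at the center". Step 7 adds "instructions to retain the email/text to present at the center". Neither step mentions another clinic. Step 9 gives intervention indexes cards too, "comparable to the standard PS arm, in case they choose to inform partners this way".

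Two other linkage tools also follow the channel. Step 6 prompts viewers of the materials for their own contact identifiers, so that they can be linked to the index. The Partner linkage paragraph sets different questions for a partner who arrives without card or message. If he was told by the materials, "we will ask him/her to identify the phone number, email address, or username to which the message was delivered". If he was told by card, "we will ask him/her to give the name or contact information of the person who gave him/her the card".

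**The concern.** All control partners are on the card route. The message route exists only in the intervention arm and is the channel under test. If a test at another clinic is easier to capture after a card than after a message, the outcome is measured with different sensitivity in the two arms. The observed risk ratio is then the true ratio multiplied by the ratio of the two capture shares, and the risk difference shifts as well. More participants would not remove this, because it is systematic. At stake is the pilot's estimate of preliminary impact, which the Statistical Analysis Plan also intends to use in sizing the later trial.

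**Working it through.** **Plan's own figure.** The Sample size and power section gives a minimal detectable difference of 26.7% for 80 vs 40 at a 30% control rate, alpha 0.05 and power 0.80. A two-sided pooled-variance calculation gives 26.6 points at 30% and 26.7 at 31%. Power at 30% vs 56.7% is 80.2%. The figure reproduces and is not in dispute. It serves below as a scale.

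**Routes to a counted test at another clinic.**
- Told by card: forwarding instructions, card collection and consent, then the database check.
- Told by message only: the database check alone.

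**Model.** The documents give none of the following shares, so all are assumed.
- e = share of tested partners who test elsewhere
- m = share of intervention partners told by message only
- c = share of tests elsewhere that the card route captures
- r = share of tests otherwise missed that the database check recovers

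Capture in control: sC = 1 - e(1-c)(1-r).
Capture in intervention: sI = 1 - e(1-r)[m + (1-m)(1-c)].
Gap: sC - sI = e × m × c × (1-r).

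**Illustration** with e = 20%, m = 80%, c = 50% and true testing of 30% in both arms:

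| r | sC | sI | Gap | Observed control vs intervention | Difference, points | sI/sC |
|---|---|---|---|---|---|---|
| 0 | 0.90 | 0.82 | 0.08 | 27.0% vs 24.6% | -2.4 | 0.911 |
| 50% | 0.95 | 0.91 | 0.04 | 28.5% vs 27.3% | -1.2 | 0.958 |
| 90% | 0.990 | 0.982 | 0.008 | 29.70% vs 29.46% | -0.24 | 0.992 |
| 100% | 1 | 1 | 0 | 30% vs 30% | 0 | 1 |

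**Range.** Write g = c(1-r) for the net deficit of messages after the database check. The spurious difference is -0.30 × e × g × m.
- Smallest: e = 10%, g = 10%, m = 50% gives -0.30 × 0.10 × 0.10 × 0.50 = -0.15 points.
- Largest: e = 40%, g = 100%, m = 100% gives -0.30 × 0.40 = -12 points. This needs a card route that captures every such test and a database that recovers none.

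**Opposite direction.** If 5% to 20% of control-arm testers could not be linked for lack of the identifiers that step 6 collects, the spurious difference would be +0.30 × 0.05 = +1.5 to +0.30 × 0.20 = +6 points, in favour of the intervention.

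**Scale.** With 80 and 40 as units, as in the plan's own calculation, and clustering of partners within index ignored, the 95% half-width of the difference is about 1.96 × √(0.3 × 0.7 × (1/80 + 1/40)) = 17.4 points.

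**The case against.** The case on the other side is substantial.

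- The database check covers both arms and does not depend on a card. If it finds every test, the gap is zero. This stands as a mitigation but cannot be taken as complete: the plan does not say which clinics the database covers, how partners are searched for, or whether negative tests are included.
- Intervention indexes also hold cards, so the difference follows channel and only partly arm. This stands, and m in the model allows for it.
- The Study design overview directs partners in both arms to the study site, and the Study site section says that newly identified MSM cases in the city are referred to the center. The first point limits e. The second helps only for positive results, and such a partner must still be linked to his index.
- The message content is provisional until the crowdsourcing events. The omission may therefore be unintended, but this is also the time to settle the wording.

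Four stronger readings are tempting, and the documents do not support them.

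1. A reader might infer that tests elsewhere count only when a card is used. The Primary outcomes section rules this out; only the active route is limited to cards.
2. A reader might infer a known bias against the intervention. The identifier prompt could favour that arm, although the Partner linkage paragraph does not say whether those entries are used to link tested partners. The net direction is therefore open.
3. A reader might take the two fallback questions as a defect in themselves. They suit their channels: a card has no receiving address, and a message that an index chose to "send through an anonymous email/phone number system" may not reveal him. Both lead to the same matching algorithm, and partner contact details are collected at baseline in both arms. Which question links better is unknown.
4. A reader might infer that the full trial would be wrongly sized. If that trial reused the same capture rules it would observe the same rates, so a sample size based on them would suit the contrast it measures. The distortion is in what the contrast is taken to mean.

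**Conclusion.** The point holds in limited form. As written, the active route to tests at other clinics is described for cards only, and message-notified partners tested elsewhere depend on a database check whose reach is not described. The primary proportion may therefore be under-captured in the intervention arm.

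Under the illustrative inputs, this element alone shifts the difference by 0 to 2.4 points, depending on database recovery. That is small beside a half-width of about 17 points. Larger shifts need extreme assumptions. Every share is assumed, so neither the size nor, once the other linkage tools are included, the net direction can be derived from the documents.

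Severity is minor: the Sample size and power section states that the pilot is not powered to compare arms. It is still worth correcting, because the outcome is primary and the remedy is simple.

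**What to change.** In the Intervention section:
- Put the same other-clinic forwarding instructions in the texts and emails as on the card.
- Have the other clinics accept the message's unique ID, with the same brief consent as for a card.
- Ask every presenting partner without an ID the same linkage questions: his own contact identifiers, and the name or contact of whoever notified him, if known.

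In the Primary outcomes section and the Statistical Analysis Plan:
- Apply the database check by one procedure in both arms, and state its coverage and search key.
- Report linked tests by capture source and arm, with the number of presenters who could not be linked.
- Keep matches made only through the step 6 identifiers in the primary count, since they may be genuine tests, and show a sensitivity analysis without them.

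The cost is minor coordination with the other clinics, one added line in the message, one common question form and a little more reporting. Some inequality will remain, because a partner notified anonymously may be unable to name the index.

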## **Index follow-up survey**

Three months after enrolment, index participants in both arms will be re-contacted by phone or email and provided a link to an online survey. A small incentive (mobile top-up) will be provided. The survey will further evaluate the acceptability and feasibility of the crowdsourced intervention among participants in the intervention group. We will also evaluate the potential challenges and advantages of the crowdsourced intervention. The survey will be comparable to the baseline survey. Sexual contact with specific partners, named previously, will be elicited, as well as new partners. The survey will also address whether the specific partners were notified by the index, underwent HIV testing, and how testing was performed.

## **Study measures and outcomes**

### **Primary outcomes**

The primary outcomes are: 1), the feasibility of the study and the feasibility of the intervention. The feasibility of the study will be measured in the ability to enroll 120 newly identified MSM HIV cases as index participants in the study center in a 12-month period, and the ability to

contact the index MSM (follow-up rate) and their partners at 3 months after enrolment (proportion of the surveyed partners response to the survey). The feasibility of the intervention will be used to measure whether the crowdsourced intervention is successfully used or carried out. This will be measured in the frequency of the partners in the intervention arm receiving the crowdsourced intervention and the frequency of the partners taking action after they receive the intervention (whether go for HIV testing). 2), the acceptability of the crowdsourced intervention: this will be measured at baseline among index participants and the partners of the index participants in the intervention arm. We will ask the index participants and their partners whether the crowdsourced intervention is acceptable to them. 3), the preliminary impact of the intervention: the proportion of partners returning for HIV testing within 3 months of the index participant's enrolment in the study, determined based on the partners presenting to the centers and those verified from the CDC electronic medical record central database.

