## Methods and study design

### Study design overview

This study will use a pilot RCT comparing the crowdsourced PS intervention to standard PS. In China, a passive referral is the only existing PS model for HIV PS. We will conduct a pilot study to refine the components and procedures of the intervention and test the feasibility and acceptability of the crowdsourced PS intervention. Newly identified MSM HIV cases will be recruited from Guangzhou. After completion of a baseline survey, eligible MSM will be randomized individually to either the crowdsourced intervention or conventional PS (control arm) in a 2:1 ratio. In both arms, partners will be instructed to report to the study site sites for HIV testing and will complete a brief sexual history questionnaire upon presentation. We will re-contact them within three months of enrolment to confirm whether the intervention or control PS procedures were implemented by the index. The primary outcome will be 1) the feasibility and acceptability of the intervention; 2) the preliminary impact of the intervention: by comparing the proportion of partners getting HIV testing between the intervention and control groups. Secondary outcomes will be the number of partners getting notified, the number of testing partners with confirmed HIV, and risk behaviors of partners. We will also observe these secondary outcomes among main male partners and casual partners separately. We hypothesize that: 1) a crowdsourced PS approach is feasible and acceptable, 2) as compared to conventional PS, will yield: a) more sexual partners reporting for HIV testing; b) more sexual partners getting notified; c) more sexual partners with confirmed HIV; and d) a set of sexual partners with greater STI risk behaviors, such as more receptive anal intercourse, and less condom use.

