## **Baseline questionnaire**

After enrolment, participants will complete a brief self-administered baseline questionnaire. Study staff will be available to assist in the event of confusion about specific questions or if participants do not have a sufficient reading level to complete the survey on a tablet. The questionnaire will address socio-demographic characteristics and HIV testing history. A more detailed, partner-centric sexual history will be obtained by focusing on sexual partners in the previous six months. The sexual history will include specific behaviors with individual partners, including receptive/insertive anal sex, performing/receiving oral sex, condom use, and frequency of each type of intercourse. Information on sexual orientation and sexual orientation disclosure status will also be collected. Detailed contact information will be obtained for the participants and sexual partners for the past six months. Contact information will include phone number, email address, WeChat ID, QQ ID, and smartphone-based sex-seeking applications ID (i.e., Blued ID).

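### Partner acceptability, a primary outcome, is timed at a baseline when no partner has yet been contacted; its likely substitute is the partners who came for testing

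*Combined protocol and SAP*

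**What the plan says.** Acceptability is the second of the three primary outcomes. The Primary outcomes section states that "this will be measured at baseline among index participants and the partners of the index participants in the intervention arm", and adds: "We will ask the index participants and their partners whether the crowdsourced intervention is acceptable to them". It names no partner instrument and gives partners no other time point.

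The data collection is described elsewhere in the protocol:

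- **Baseline questionnaire:** "After enrolment, participants will complete a brief self-administered baseline questionnaire". These are the enrolled index men.
- **Intervention:** once the intervention has been introduced to the participants in that arm, "a short survey that aims to evaluate the feasibility and acceptability of the crowdsourced intervention will be carried out". Partners are not mentioned.
- **Study design overview:** partners "will complete a brief sexual history questionnaire upon presentation".
- **Index follow-up survey:** the 3-month survey goes to index participants in both arms.

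The same section gives three partner measures of feasibility: 3-month contact, as the "proportion of the surveyed partners response to the survey"; receipt, as the "frequency of the partners in the intervention arm receiving the crowdsourced intervention"; and action, as "the frequency of the partners taking action after they receive the intervention", meaning whether they go for testing. The Statistical Analysis Plan says only that feasibility and acceptability will be described. It gives no denominator and no rule for non-response.

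**The concern.** A partner can judge the materials only after they reach him. Materials are chosen and sent after randomization, and under step 3 of the Intervention section the index may wait up to 6 weeks before asking for them to be sent. At the index's baseline there is nothing for the partner to rate, so the timing rule cannot be followed.

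Site staff will then use the contact they do have, which is the visit for testing. A man who comes for testing has already responded as the intervention intends. Acceptability measured only in such men is selected on a favourable outcome.

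This matters because the Sample size and power section says the trial is not powered to compare the arms, and the Randomization section justifies the 2:1 ratio partly by the wish to measure feasibility and acceptability. Those outcomes carry much of the pilot's purpose.

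**Working it through.** **1. Can the outcome be collected as written?** The order of events in the protocol is: index enrolment, index baseline questionnaire, randomization, explanation of the procedures, choice of material and delivery route, sending (immediately or within 6 weeks), viewing by the partner, and presentation for testing. Partner acceptability is placed at the second event. The earliest event at which a partner can answer is viewing. At that point, step 6 of the Intervention section asks him only for contact identifiers. The next is presentation, where the questionnaire covers sexual history. No described instrument asks a partner about acceptability at a time when he could answer.

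**2. The plan's own figure.** The only design calculation is the minimal detectable difference of 26.7 points from a control return rate of 30%, with 40 and 80 participants, alpha 0.05 and power 0.80. The point does not depend on it, but it supplies the 56.7% used below. With the pooled two-proportion formula (two-sided):

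- average proportion = (0.30 + 2 × 0.567)/3 = 0.478
- n (control) = [1.96 × √(0.478 × 0.522 × 1.5) + 0.842 × √(0.30 × 0.70 + 0.567 × 0.433/2)]² / 0.267² ≈ 39.8, so 40

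Solved the other way, 40 and 80 give 26.6 points, and power at 30% against 56.7% is 0.802. The figure reproduces.

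**3. What a figure from presenting partners says about all partners.** Let r be the share of partners asked and a the acceptance among those asked. If none of the others accept, acceptance is r × a; if all do, it is r × a + (1 − r). The r values are the plan's return rates; a = 0.90 is an assumption.

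| Share asked (r) | Reported | Lower bound | Upper bound |
|---|---|---|---|
| 30% | 90% | 0.30 × 0.90 = 27% | 0.27 + 0.70 = 97% |
| 56.7% | 90% | 0.567 × 0.90 = 51% | 0.51 + 0.433 = 94% |

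**4. The same among recipients only.** Suppose 30% of reported partners test, all of them received the materials, and only they are asked.

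- If an assumed 50% received the materials, the share asked among recipients is 0.30/0.50 = 60%. Bounds: 0.60 × 0.90 = 54% to 0.54 + 0.40 = 94%.
- If an assumed 70% received them, the share asked is 0.30/0.70 = 43%. Bounds: 0.429 × 0.90 = 39% to 0.386 + 0.571 = 96%.

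The range is narrower than in step 3 but still wide.

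**5. The action measure.** This is the share tested among all reported partners divided by the share who received the materials, again if all who tested were recipients. With 30% tested overall, it is 0.30/0.50 = 60% or 0.30/0.70 = 43%. It answers a legitimate question, but it leaves out partners who were never reached.

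**6. What cannot be computed.** Partners per index, the share receiving the materials, and acceptability in any group are not in the documents. The size of the actual bias therefore cannot be derived.

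**The case against.** The strongest reply is that this is loose timing in a descriptive pilot outcome, and that the study has means of reaching partners who do not test. Much of that is right:

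- Partner contact details are taken from the index at baseline, and viewers can be linked to the index before any test.
- The index reports on each named partner's notification and testing at 3 months.
- The Data management section mentions a survey for partners, without content or timing. The Study design overview speaks of re-contact within three months in a sentence whose subject could be the partners. A partner survey may be intended.

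These sources show that non-testers could be asked. They record identity, viewing, notification and testing; nothing says that a partner who does not present will be asked about acceptability.

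A reader might go further and infer that all the partner feasibility measures use responders as their own denominator and will be inflated. The documents do not support that. Surveyed partners may simply mean those sent the survey, which gives an ordinary response rate; the defect is that the term is undefined. Receipt refers to partners in the intervention arm. Action is conditional on receipt, not on response: a poorly accepted message would lower it, and testing can be checked against the CDC record and the index's report.

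Nor do the documents make partner acceptability the basis for moving to a full trial. They state no progression criteria.

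It is also a fair objection that acceptability over all named partners mixes reach with acceptability, since a man who never received the materials cannot rate them. The fix therefore reports it among recipients or viewers and shows reach separately.

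**Conclusion.** The point holds in limited form. Partner acceptability cannot be collected at the time stated, and no usable instrument is described. If presenting partners are used by default, the estimate is likely to be optimistic, by an unknown amount. The ranges of 27% to 97% and 51% to 94% are illustrations. They rest on an assumed 90% acceptance, on no other partner being asked, and, for the first, on a control-arm rate applied to an outcome measured only in the intervention arm.

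The 3-month partner-contact measure lacks a defined denominator and a clear procedure, and the action measure needs a companion over all reported partners. Enrolment, index follow-up, index acceptability and the proportion of partners tested are not affected. The change is worth making because it is cheap and reduces selection on the favourable outcome.

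**What to change.** - In Primary outcomes, delete the baseline timing for partners and keep it for index participants.
- Ask partners one acceptability item at the viewing step (Intervention, step 6) and again at presentation.
- Report partner acceptability among those who viewed or received the materials, with the number not asked and worst- and best-case bounds.
- For intervention-arm partners, report the counts reported, sent to, viewing and tested. Give testing over all reported partners beside testing after receipt.
- Define the 3-month measure as partners who respond divided by partners with contact details whom the study tried to reach, and say how they are approached; otherwise drop it.

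The cost is one extra question on a step that already exists, some protocol and SAP wording, and headline percentages that will probably be less favourable.
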